### 2.2 Secondary Objective(s)

- **Determine whether gene polymorphisms in VDR and CYP27B1 are predictive for the degree of responsiveness to Vitamin D as a neoadjuvant for PDT.**

#### **Aim 1: Is there a correlation between Vitamin D receptor (VDR) polymorphisms and PDT treatment outcomes for actinic keratoses with and without prior Vitamin D supplementation?**

Leukocyte DNA will be collected to assess the relationship between VDR polymorphisms and treatment response in patients undergoing photodynamic therapy for actinic keratoses. Patients

[figure not shown]
will be genotyped to determine the presence of F/f and L/S alleles. These findings will be correlated with the therapeutic responsiveness to ALA-PDT, with or without vitamin D enhancement.

These studies propose to test and demonstrate that vitamin D3 pretreatment can be used to enhance porphyrin accumulation and PDT efficacy in the treatment of AKs. PDT is approved by the FDA for the field treatment of widespread precancerous lesions of the skin. In Europe, PDT is also approved for the treatment of squamous cell carcinoma and basal cell carcinoma of the skin. We expect this clinical trial to support the foundation for a new treatment modality, vitamin D3-enhanced PDT, for the treatment of AKs and other nonmelanoma skin cancers. This data would benefit public health by demonstrating this approach to be a simple, safe, and effective treatment for AKs, as well as supporting its use as a nonscarring alternative to surgery for early squamous cell carcinomas and basal cell carcinomas.

### 3.0 STUDY DESIGN

#### 3.1 Study Design Protocol

This is a non-randomized interventional trial, in which the study group will be compared to a baseline cohort of patients from a previous study (IRB 16-1615) who received the same regimen of PDT, but without any Vit D. Our protocol is shown in Fig. 5. The dose of D3 chosen for this study reflects the best currently available evidence regarding efficacy, safety, and practicality of oral D3 dosing. In our mouse studies, the human equivalent of 10,000 IU given daily for 10 d, provided better PpIX enhancement than 5,000 IU/d x 10 d, with no evident toxicity [12]. In normal mice, 3 d of daily 10,000 IU were just as good as 10 d for boosting PpIX levels in tumors; however, the 3-day regimen worked only about half as well in VD-deficient mice (prelim data; Fig. 4). Importantly however, 10 d were sufficient to restore the PpIX elevating effect in VD deficient animals (Fig. 4). Therefore, we will tailor the neoadjuvant D3 dose in this clinical trial, according to initial serum 25OH-D3 levels, to maximize convenience and safety, while testing for equivalence of therapeutic benefit. Specifically, study patients with normal VD levels will take a daily 10,000 IU D3 pill for 3-5 d, while patients with suboptimal VD levels will take the D3 pill for 10-14 d. (Ranges are given to compensate for patients possibly missing a day or two). Regarding safety, the doses of D3 that physicians use to treat VD deficiency can be remarkably high, including 5,000 IU (oral, daily, continuous), 50,000 IU (oral, twice weekly for 5 weeks), and 500,000 IU (i.m., single dose); all are reported safe and effective[34]. Our dosing regimen is well within these safe ranges.

**Figure 5. Study Design.**

At **Visit 1**, patients will be given oral D3 to take for either 5 days or 14 days (according to their normal or deficient 25OH-D3 level, respectively) prior to the PDT treatment at **Visit 2**. Mandatory F/U visit at 3 months (**Visit 3**). After that, patients will be followed clinically every 6-12 months.

Study patients will have three mandatory visits. At Visit #1, patients will sign the ICF and have their blood drawn. A vitamin D-relevant history will be taken, and CIS lesions counted by a clinician. The patient will be given enough D3 pills (10,000 IU each) to be taken daily at home, beginning at either day -5 or day -14, as per their assignment (see above). At Visit #2, to assess how much PpIX is generated in the skin, ten lesions will be measured using our fluorescence probe dosimeter (before and after ALA application). PDT will then be performed. At Visit #3 (which is 3-6 months after PDT), the patient's lesions will be counted to assess the treatment response).

#### 3.2 Number of Subjects

A total of 30 patients with at least 10 AKs will be needed to complete the study.

### 3.3 **Replacement of Subjects**

If a study subject withdraws for any reason, up to 6 months after the start of this study, then a new subject can be recruited in his/her place.

### 3.4 **Expected Duration of Subject Participation**

#### 3.4.1 *Duration of Therapy*

The study consists of a single blood draw, to be collected by routine phlebotomy on the day of PDT treatment or within 1 week of the treatment.

The principal investigator reserves the right to temporarily suspend or prematurely discontinue this study. The date and reason for discontinuation will be documented. Every effort will be made to complete the appropriate assessments.

#### 3.4.2 *Duration of Follow Up*

Patients will be followed for 3 months, as specified in the study Calendar; see **section 11.0**. The treatment (PDT) will occur at Visit 2, followed at 3 months by a follow-up evaluation (within a window extending from 3-6 months after Visit 2) .

#### 4.0 PATIENT SELECTION

This section shows a checklist of criteria (sections 4.1 to 4.3) that must be met in order for a patient to be considered eligible for this study. A checklist with this information will be used to confirm a patient's eligibility. It will be completed for each patient, then signed and dated by the treating physician, and a nurse or physician unaffiliated with the principal investigator, as shown below.

PATIENT'S NAME \_\_\_\_\_

MEDICAL RECORD # \_\_\_\_\_

A) SIGNATURE OF PERSON DETERMINING ELIGIBILITY \_\_\_\_\_ DATE: \_\_\_\_/\_\_\_\_/\_\_\_\_  
mm dd yyyy

B) SIGNATURE OF PERSON CONFIRMING ELIGIBILITY: \_\_\_\_\_ DATE: \_\_\_\_/\_\_\_\_/\_\_\_\_  
mm dd yyyy

C) INVESTIGATOR SIGNATURE: \_\_\_\_\_ DATE: \_\_\_\_/\_\_\_\_/\_\_\_\_  
mm dd yyyy

#### 4.1 Inclusion Criteria

4.1.1 Patients can be males or females of at least 18 years of age. Patients need to have actinic keratoses in sufficient numbers (>10) to warrant PDT therapy in our clinic.

#### 4.1.2 *Female subjects must not become pregnant during the study*

The effects of 5-aminolevulinic acid (Levulan™) on the human fetus are unknown. For this reason, women of child-bearing potential must agree to use contraception (double barrier method of birth control or abstinence) prior to study entry, and throughout study participation. Should a woman become pregnant or suspect that she is pregnant while she is participating in this study, she should inform the treating physician immediately.

4.1.3 Subjects must be **able** to understand and **willing to sign a written informed consent document**.

#### 4.2 Exclusion Criteria

4.2.1 Pregnant or nursing.

4.2.2 At risk for hypercalcemia (renal disease, sarcoidosis, etc.)

4.2.3 Using topical retinoids, since these can exacerbate the post-PDT erythema reaction.

4.2.4 Using any topical treatment on their AKs; must stop at least one month prior.

4.2.5 Currently undergoing treatment for other cancers with medical or radiation therapy.

4.2.6 Patients with a known hypersensitivity to 5-aminolevulinic acid or any component of the study material.

4.2.7 Patients with history of a photosensitivity disease, such as porphyria cutanea tarda.

4.2.8 Currently participating in another clinical trial.

#### 4.3 Inclusion of Women, Children, and Minorities

Men and women at least 18 years of age of any ethnic group are eligible for this trial, as long as they fulfill the eligibility criteria.

## **5.0 REGISTRATION**

### **5.1 Recruitment**

Patients who have been scheduled to receive PDT in our dermatology clinics will be given written information prior to their visit, including a copy of the Informed Consent (IC) that describes the purpose of the study. If the patient indicates that he/she is interested, the physician or study nurse will review the IC with the patient on the day of PDT and answer all questions. After the patient signs the IC, the patient will be directed to the phlebotomy lab in the Crile building (Crile A1) to have blood drawn.

### **5.2 Consent:**

When a patient is referred for the study, he/she will be given information about the study and all its components. An Informed Consent will be mailed to the patient at least 72 h prior to the first visit. If the patient continues to be interested in the study, he/she will be scheduled for the first visit in Dermatology. Once the patient arrives in clinic, the study will be explained once again. If the patient indicates understanding and wishes to enroll in the study, he will be asked to sign the consent form with the understanding that he can change his mind at any time during the study. The informed consent must be signed by the patient, and by a parent or legal guardian if the patient is a minor, and witnessed. The participant will be given contact phone numbers to call if questions arise as the study proceeds.

### **5.3 Randomization:**

There will be no randomization procedures.

## **6.0 TREATMENT PLAN**

**6.1. VISIT 1:** As part of the Informed Consent process, the patient will be seen in the clinic for a full screening visit (**Visit 1**), including a review of medical records and a physical exam. Informed Consent will be obtained on-site. AK lesions will be carefully evaluated to determine if the patient meets eligibility criteria (> 10 AK lesions). A study nurse from the CRU will draw two tubes of blood, one for serum D3 assay, the other for leukocyte collection (buffy coat) and preparation of DNA. The patient will be sent home after scheduling the date of the next visit, in approximately 1 month.

**Evaluation procedures at Visit 1:** Blood will be collected in two tubes: one with an anticoagulant (e.g. heparin) and the other without. The nonheparinized tube will be sent to CCF Clinical Laboratory Medicine for routine measurement of vitamin D (calcidiol) serum levels. The heparinized tube will be transported to [name] laboratory for preparation of leukocyte DNA (see Procedure B).

**VISIT 2: Treatment procedure:** The patient will return on the treatment day, and all AK lesions will be carefully marked with a water-soluble pen, photographed and mapped. PDT will then be conducted as per our routine procedure, as follows. The prodrug (5-aminolevulinic acid, 5-ALA; Levulan® Kerastick™, 20% Topical Solution) is applied to the entire involved area of skin, allowed to dry, and left on the skin surface for a period of time between 15 to 30 min (for AK of the face and scalp). During that time, the 5-ALA prodrug is selectively absorbed by preneoplastic cells and is converted within the cells' mitochondria into protoporphyrin IX (the molecule that constitutes the actual phototarget). The patient is positioned under the light source (Blu-U, 400 nm wavelength), wearing protective yellow goggles, and is illuminated for 30 min. Upon completion of PDT, aftercare steps are explained to the patient, and then the patient is sent home with emollient samples and written aftercare instructions. A questionnaire of side effects during the 6 days post-PDT will be filled out at home.

**Visit 3: Final evaluation visit (3 months post-PDT):** AK lesions will be counted and photographed.

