## **7.0 DOSING DELAYS / DOSE MODIFICATIONS**

In photodynamic therapy, two types of dosing must be considered: (1) the dose of prodrug; (2) the dose of light. The prodrug, Levulan™, is a liquid preparation with a fixed concentration of 20% aminolevulinic acid (ALA) that is delivered topically as a uniform film that dries upon application to the skin. The delivered dose of ALA cannot be changed, but the effective concentration of the photosensitizer (PpIX) in the skin can be controlled by shortening or lengthening the incubation time. Once ALA has been converted into PpIX within the tumor cells, PpIX is activated by shining the light (either blue or red wavelengths). Photons are delivered from an FDA-approved light source (Blu-U™ for blue light at 400 nm; Aktelite™ for red light at 635 nm) at a fixed dose rate, measured in Joules/m^2/sec. The product of the dose rate and the illumination time gives the final light dose. The light dose that is safe and effective for treatment of actinic keratosis using a continuous blue light illumination protocol is 20 J/cm^2 (Kaw, [name] et al, J Am Acad Dermatol, 2019, in press). In the proposed study, all AKs will be treated with blue light at 20 J/cm^2, following a standardized ALA incubation time of 30 minutes prior to illumination.

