## **11.0 STUDY PARAMETERS AND DETAILED STUDY CALENDAR**

Each step of the study has been described in detail under Section 6.0, “Treatment Plan”. Each study visit, and events occurring between visits, are laid out in the Table in section 11.6 (“Calendar”).

**Allowances for variations in scheduling:** A visit window of **3 months** is allowed when scheduling the final follow-up assessment visit.

In brief, the study consists of the following activities:

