### **11.3 PDT treatment (Visit 2)**

All AK lesions are measured clinically and photographed. Noninvasive fluorescence dosimetry may be performed on up to 6 lesions. *Levulan KerastickTM* will be applied to each lesion and left to incubate for 30 minutes. **Blue light** (Blu-U device, 20 J/cm^2, 33 minutes) will be administered.

11.4 **At home:** Study nurse will call patient to check up on the patient and record side effects at 24-48 h.

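### Section 6.1's ALA and light times conflict with sections 7.0 and 11.3, and the protocol sets no single PpIX sampling schedule

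*Combined protocol and SAP*

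**What the plan says.** **Incubation and light.** Under section 6.1 (Visit 2), ALA is "left on the skin surface for a period of time between 15 to 30 min (for AK of the face and scalp", after which the patient "is illuminated for 30 min". No light dose is given there. Section 7.0 sets 20 J/cm² for all AKs, "following a standardized ALA incubation time of 30 minutes prior to illumination". Section 11.3 agrees on incubation (ALA is "left to incubate for 30 minutes") and ties 20 J/cm² to an exposure time; its light entry ends "33 minutes) will be administered". The calendar in section 11.6 gives 20 J/cm² without a time.

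**Which section governs.** Section 11.0 sends the reader back to the treatment plan: "Each step of the study has been described in detail under Section 6.0".

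**PpIX measurement.** Section 3.1 (text with Figure 5) says that ten lesions will be read, before and after ALA. Section 11.3 makes dosimetry optional, on six lesions at most. Subaim 1a in section 2.1, the calendar and section 12.2.2 place the reading 30 minutes after ALA. Sections 1.7 and 2.1 include normal skin; sections 3.1, 11.3, 11.6 and 12.2.2 do not mention it. The Visit 2 text in section 6.1 contains no PpIX step.

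**The concern.** The section named as the detailed source is the loosest of the set. Staff who follow section 6.1 as written may turn the light on at any time from minute 15, before the PpIX reading is due. Section 9.1 says that illumination destroys PpIX, so a reading taken after the light has started is not the quantity that section 12.2.2 defines.

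PpIX accumulation is the mechanism in the primary hypothesis (section 2.0). It is subaim 1a under the primary objective and a listed secondary objective in section 14.0. Section 7.0 states that the effective PpIX concentration "can be controlled by shortening or lengthening the incubation time", so a permitted range of 15 to 30 min can add variation to this endpoint. With the lesion number unsettled as well, the endpoint may be missing for some patients and rest on different numbers of readings in others.

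There is a further, weaker concern. The trial is not randomized, and section 3.1 relies on the IRB 16-1615 controls having had identical PDT. A protocol that does not state one PDT regimen cannot show that the two groups were treated alike.

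**Working it through.** **1. The statements side by side**

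| Section | ALA incubation | Light | PpIX reading |
|---|---|---|---|
| 1.7 | – | – | lesional and normal skin; no number or time |
| 2.1, subaim 1a | – | – | 30 min after ALA; lesional and normal skin |
| 3.1 | – | – | ten lesions, before and after ALA |
| 6.1 | 15–30 min | 30 min, no J/cm² | none |
| 7.0 | 30 min | 20 J/cm², no time | – |
| 11.3 | 30 min | 20 J/cm² over 33 min | optional, at most six lesions |
| 11.6 calendar | – | 20 J/cm², no time | selected lesions at 30 min |
| 12.2.2 | – | – | 30 min after ALA |

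The 33 min figure appears only in section 11.3; 20 J/cm² appears in 7.0, 11.3 and 11.6.

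**2. Light dose**

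Section 7.0 describes a fixed dose rate and gives the rule: "The product of the dose rate and the illumination time gives the final light dose". So dose = rate × time. The lamp's irradiance is not stated, so both possibilities are worked.

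- If 33 min delivers 20 J/cm² (section 11.3): rate = 20 / (33 × 60 s) = 10.1 mW/cm². Then 30 min delivers 20 × 30/33 = 18.2 J/cm², a shortfall of 1 − 30/33 = 9.1%.
- If 30 min delivers 20 J/cm²: rate = 20 / (30 × 60 s) = 11.1 mW/cm². Then 33 min delivers 20 × 33/30 = 22.0 J/cm², an excess of 33/30 − 1 = 10%.

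Under either assumption, the two times cannot both give 20 J/cm².

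**3. Timing of the PpIX reading**

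Take ALA application as minute 0. Under section 6.1 the light may start at minute 15 and run for 30 min, to minute 45. Minute 30 then falls (30 − 15)/30 = 50% of the way through the exposure. For any start before minute 30, the 30-minute reading cannot be taken before light. Only the upper end of section 6.1's range is compatible with sections 2.1, 11.6 and 12.2.2.

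**4. Amount of PpIX data per patient**

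Section 3.1: ten lesions, each read before and after ALA, so 10 × 2 = 20 lesional readings. Section 11.3: anywhere from no lesions to six, at most 6/10 = 60% of the lesion number in 3.1. The calendar's wording fits either number.

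**5. Sample size**

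This point does not touch it. The SD of a paired difference is 24 × √(2 × (1 − 0.1)) = 32.2, and a paired t-test for a 20-point difference with n = 30 has power 0.908. This agrees with the 30 patients and 90% in section 14.0.

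**The case against.** The intended regimen can be inferred. Section 7.0 speaks specifically of this study, and 11.3 agrees with it on incubation and dose. Section 6.1 presents its steps as the clinic's usual practice, so its range could be read as background, and its 30 min of light carries no dose that could contradict 20 J/cm². The light discrepancy is small and conditional on an unstated irradiance. PpIX is not the primary outcome (the protocol summary lists it as exploratory), and the mixed models in section 14.0 accept unequal lesion counts. The calendar marks the PpIX measurement at Visit 2, and subaim 1a treats it as planned, so taking no reading at all is the extreme interpretation of section 11.3. Some of the differences are omissions rather than contradictions.

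Much of this stands as a limit on weight. The light gap alone would be minor, sample size and power are unaffected, and no clinical effect of 18.2 versus 20 J/cm² can be derived from the documents. It does not remove the point. Section 6.1 is the treatment plan for Visit 2, and section 11.0 directs readers to it. Mixed models tolerate unequal numbers of lesions, but they cannot recover a reading that early light precluded or that was never taken.

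**Conclusion.** The concern holds and should be corrected before enrolment. The main consequence is for the PpIX endpoint: section 6.1 permits a sequence that precludes the required 30-minute reading, and the number of lesions read per patient may be ten, or anything from none to six, depending on the section followed. The permitted incubation varies by a factor of two (15 to 30 min). The light-dose conflict is 9% to 10%, assuming the fixed dose rate described in section 7.0 and that one of the two stated times does deliver 20 J/cm².

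A mismatch with the IRB 16-1615 controls is a possible risk to the primary comparison, not a demonstrated bias. The documents give neither the controls' incubation and illumination times nor a dose-response, so its size and direction cannot be computed.

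**What to change.** 1. First confirm the incubation time, light dose and illumination time that the IRB 16-1615 controls received. Then amend section 6.1 to 30 min of ALA and 20 J/cm² with the matching illumination time (33 min according to section 11.3).
2. Record the actual incubation and illumination minutes for every patient.
3. Set one required PpIX schedule and state it identically in sections 3.1, 6.1, 11.3, 11.6 and 12.2.2: a single lesion number, the pre-ALA reading already planned in 3.1, the 30-minute reading completed before light, and an explicit decision on whether normal skin is measured. Analysing the ALA-induced change is optional.

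The cost is wording in five places, two recorded times per patient and one check of the same group's earlier study. No visit or new kind of procedure is added, since each reading is already written somewhere in the protocol. Making the readings mandatory does add some Visit 2 work compared with section 11.3. Readings not taken at that visit cannot be recovered later.

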### **6.2 Duration of Therapy**

The target duration of therapy **3 months**. In the absence of treatment delays due to adverse events, treatments may administered unless one of the following criteria applies:

- (i) Intercurrent illness prevents administration of treatment.
- (ii) The investigator considers it, for safety reasons, to be in the best interest of the patient.
- (iii) Unacceptable adverse event(s), including: general or specific changes in the patient's condition render the patient unacceptable for further treatment in the judgment of the investigator; patient decision to withdraw from treatment (partial consent) or from the study (full consent); pregnancy during the course of the study for a child-bearing participant; death. The Principal Investigator reserves the right to temporarily suspend or prematurely discontinue this study.

### **6.3 Duration of Follow Up**

Patients will be followed for 3 months, as specified in the study Calendar; **section 11.0**. The single treatment will occur at Visit 2, at 3 months prior to the last visit. No formal study follow-up is planned after completion of 3 months, but every effort will be made to encourage patients to return at 6 month intervals for 2 years for routine examination, at which time will document AK status (clearance/recurrence) in our PDT database registry, and provide additional standard-of-care as needed.

## **7.0 DOSING DELAYS / DOSE MODIFICATIONS**

In photodynamic therapy, two types of dosing must be considered: (1) the dose of prodrug; (2) the dose of light. The prodrug, Levulan™, is a liquid preparation with a fixed concentration of 20% aminolevulinic acid (ALA) that is delivered topically as a uniform film that dries upon application to the skin. The delivered dose of ALA cannot be changed, but the effective concentration of the photosensitizer (PpIX) in the skin can be controlled by shortening or lengthening the incubation time. Once ALA has been converted into PpIX within the tumor cells, PpIX is activated by shining the light (either blue or red wavelengths). Photons are delivered from an FDA-approved light source (Blu-U™ for blue light at 400 nm; Aktelite™ for red light at 635 nm) at a fixed dose rate, measured in Joules/m^2/sec. The product of the dose rate and the illumination time gives the final light dose. The light dose that is safe and effective for treatment of actinic keratosis using a continuous blue light illumination protocol is 20 J/cm^2 (Kaw, [name] et al, J Am Acad Dermatol, 2019, in press). In the proposed study, all AKs will be treated with blue light at 20 J/cm^2, following a standardized ALA incubation time of 30 minutes prior to illumination.

